5.2.1 Duration of Exposure to Trial Medication

Duration of exposure to each treatment of each subject will be summarized for subjects who enrolled in Optional Tolvaptan Treatment Component. A subject's duration of exposure is defined as the trial medication end date - trial medication start date + 1.

5.2.2 Adverse Events

Definitions:

- A treatment-emergent adverse event (TEAE) is an event that is observed or reported after administration of trial medication in this trial that was not present prior to trial medication administration or an event that represents the exacerbation of a pre-existing event. Exacerbation includes any event that increases in frequency or severity or becomes classified as serious after the start of treatment in this trial.
- An adverse withdrawal is a subject who withdrew from the trial due to an AE.
- A serious adverse event (SAE) is an AE that is classified as serious according to the criteria specified in the trial protocol.

The incidence of the following events will be summarized:

AEs and TEAEs

AEs and TEAEs by severity

TEAEs potentially causally related to the IMP

AEs and TEAEs with an outcome of death

Serious AEs and TEAEs

AEs and TEAEs leading to discontinuation

All AEs will be coded by MedDRA (Medical Dictionary for Regulatory Activities) system organ class and preferred term.

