3.1.1 Core Safety Follow-up Component

The core safety follow-up component of the trial is a 6-month period in which pediatric subjects (children and adolescents) with dilutional (euvolemic or hypervolemic) hyponatremia who previously participated in a tolvaptan hyponatremia trial will be followed (at a clinical trial site and/or through telephone calls), regardless of the need for treatment for hyponatremia, to assess the long-term safety of tolvaptan. There is no screening phase.

Enrollment into this trial should follow completion or discontinuation from the previous tolvaptan hyponatremia trial; the subject must have been off investigational medicinal product (IMP) for at least 7 days between trials. A longer lapse between completion of the previous tolvaptan hyponatremia trial and enrollment into this trial is permitted while enrollment is open.

The final laboratory assessments for liver function tests (LFTs) from the previous tolvaptan trial can serve as the baseline laboratory assessments for this trial if the values are within the normal range, and collected within 30 days of the baseline visit for this trial. However, LFTs for these subjects will be collected at Month 1 or Month 2 at a clinical site visit or local laboratory. If LFTs from the previous tolvaptan trial are abnormal, or collected > 30 days of the baseline visit of this trial, they will be assessed at baseline.

The last assessments in the previous tolvaptan trial will serve as the baseline assessments if collected within 30 days of enrollment into this trial. Otherwise, assessments will be repeated if > 30 days have lapsed since the previous tolvaptan trial.

Subjects enrolled in this trial will be assessed up to 7 times over the 6 month core safety follow-up component of the trial. The baseline and the Month 6/Early Termination (ET) visits are performed in the clinic, while assessments during Months 1, 2, 3, 4 and 5 will be conducted by telephone, unless LFTs are required at Month 1 or Month 2. During the in-clinic visits, subjects are evaluated for relevant trial information.

Baseline Visit

All subjects will attend the clinic for the baseline visit.

Months 1, 2, 3, 4 and 5

All subjects will receive telephone assessments for Months 1, 2, 3, 4, and 5. If LFTs are required at Month 1 or Month 2, the subject may obtain these results through a clinic visit or from a local laboratory.

Month 6/End of Trial Visit

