7.6 Safety Analyses

7.6.1 Adverse Events

All AEs will be coded by system organ class and Medical Dictionary for Regulatory Activities (MedDRA) preferred term. The incidence of the following events will be summarized for all subjects (AEs), and all subjects receiving tolvaptan (treatment-emergent AEs [TEAEs]):

- AEs and TEAEs
- AEs and TEAEs by severity
- TEAEs potentially causally related to the IMP
- AEs and TEAEs with an outcome of death
- Serious AEs and TEAEs
- AEs and TEAEs leading to discontinuation

The above summaries will also be prepared for TEAEs potentially causally related to the IMP.

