9.2 Data Collection

During each subject's visit to the clinical trial site, a clinician participating in the trial will record progress notes to document all significant observations. At a minimum, these notes will contain:

- Documentation of the informed consent process, including any revised consents;
- Documentation of the investigator's decision to enroll the subject into the trial, the review of all inclusion/exclusion criteria prior to tolvaptan administration, and confirmation of the subject's actual participation in the trial;
- The date of the visit and the corresponding Visit or Day in the trial schedule;
- General subject status remarks, including any *significant* medical findings. The severity, frequency, duration, action taken, and outcome of any AEs and the investigator's assessment of relationship to tolvaptan must also be recorded;
- Any changes in concomitant medications or dosages;
- A general reference to the procedures completed;
- The signature (or initials) and date of each clinician (or designee) who made an entry in the progress notes.

In addition, any contact with the subject via telephone or other means that provides significant clinical information will also be documented in the progress notes as described above. Any changes to information in the trial progress notes, and other source documents will be initialed and dated on the day the change is made by a site trial staff member authorized to make the change. Changes will be made by striking a single line through erroneous data (so as not to obliterate the original data), and clearly entering the correct data (eg, ~~wrong data~~ right data). If the reason for the change is not apparent, a brief explanation for the change will be written in the source documentation by the clinician. If electronic data systems are being utilized, a full audit trail of changes must be maintained.

Information from the trial progress notes and other source documents will be promptly and LEGIBLY transcribed to eCRFs for transmission to the sponsor. Changes will be entered by investigative site personnel directly onto electronic CRFs in the sponsor's electronic data capture (EDC) system. Changes to the data will be captured by an automatic audit trail.

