5.2 Safety Analysis

Due to the early termination status, not all planned safety analyses will be provided due to lack of data. For an example, no subject received optional Tolvaptan treatment, the safety analyses specified in the SAP will not be applied to Optional Tolvaptan Treatment Component.

Safety variables to be analyzed include adverse events (AEs), clinical laboratory data, and vital signs. In general, summary statistics will be provided for safety variables based on all available data.

Baseline of the subjects receiving tolvaptan in the Optional Tolvaptan Treatment Component is the last evaluation prior to the first dose at each cycle in the Optional Tolvaptan Treatment Component. Baseline of the subjects participating in the Core Safety Follow-up Component is the last evaluations from the previous trial (tolvaptan in Trial 156-08-276), if the last evaluation was done in previous trials within one month of this trial starts. If more than one month passes between trials, the baseline will be the evaluations at the baseline visit of this trial.

Safety analyses by age categories (≥ 4 weeks to < 4 years, ≥ 4 years to < 8 years, ≥ 8 years to < 12 years, ≥ 12 years to < 18 years) will be provided. Safety analysis by underlying etiology (heart failure, hepatocellular disease, SIADH/other) will also be provided.

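### The relatedness summary covers only TEAEs, which need a dose in this trial; no subject was dosed, so recorded causality for core adverse events reaches no planned summary or listing

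*SAP*

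**What the plan says.** **SAP 5.2.2** lists the incidence summaries for adverse events. Overall incidence, severity, fatal outcome, seriousness and discontinuation are each given for AEs and TEAEs together. The relatedness line reads "TEAEs potentially causally related to the IMP".

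The same section defines a TEAE: "A treatment-emergent adverse event (TEAE) is an event that is observed or reported after administration of trial medication in this trial". Worsening of a pre-existing event also counts, but that clause is tied to treatment in this trial too, ending with an event that "becomes classified as serious after the start of treatment in this trial".

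**SAP 5.2** states that "no subject received optional Tolvaptan treatment" and that the planned safety analyses will therefore not be applied to the optional component.

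**Protocol 7.6.1** has the same split. AEs are summarised for all subjects and TEAEs for those receiving tolvaptan. It has one relatedness line, restricted to TEAEs, and a closing sentence: "The above summaries will also be prepared for TEAEs potentially causally related to the IMP".

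**Protocol 5.1** defines the Related / Not Related judgement for an AE, without limiting it to treatment-emergent events. **Protocol 9.2** requires that, for any AE, the investigator's "assessment of relationship to tolvaptan must also be recorded".

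**Protocol 3.1.1** says subjects are followed in the core component, whatever their need for treatment, "to assess the long-term safety of tolvaptan".

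**The concern.** Treatment emergence is the usual basis for a relatedness table when the exposure of interest is given during the trial. In the core component it is not: subjects enter after an earlier tolvaptan trial, having been off study drug for at least 7 days. An event during these 6 months that an investigator attributes to tolvaptan is just what a post-treatment follow-up should be able to report. The plan collects that judgement and then limits its only use to events that cannot occur in an undosed subject.

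At stake is the causality part of the safety report for the core component, which after early termination is the only component with data. Core AEs would be reported by severity, seriousness, outcome of death and discontinuation, with nothing to show which of them investigators considered related. In children with heart failure, liver disease or other serious underlying conditions, many events will reflect the disease, so the investigator's attribution carries information.

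**Working it through.** No sample size, power or error rate is involved. The check sets each planned line against the population that can contribute to it.

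**Inputs**
- Subjects dosed in this trial: 0 (SAP 5.2; SAP 5.1 says the same).
- TEAE: needs trial medication in this trial, including under the worsening clause (SAP 5.2.2).
- AE population: all subjects. TEAE population: subjects receiving tolvaptan (Protocol 7.6.1).
- Causality: defined for AEs generally (Protocol 5.1) and recorded for any AE (Protocol 9.2).

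**Step 1: can an undosed subject have a TEAE?** Both routes in the definition depend on treatment in this trial, so no. Subjects with a TEAE ≤ subjects dosed = 0. Hence TEAEs = 0, and related TEAEs ≤ TEAEs = 0, whatever investigators recorded.

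**Step 2: what each SAP 5.2.2 line yields**

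| Summary line | Covers core AEs? | Shows causality? |
|---|---|---|
| Overall incidence | Yes | No |
| Severity | Yes | No |
| Relatedness | No (TEAEs only) | Yes, but with 0 events |
| Death | Yes | No |
| Serious | Yes | No |
| Discontinuation | Yes | No |

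Lines covering core AEs: 6 − 1 = 5. Lines showing causality: 1. Lines doing both: 0 of 6. Protocol 7.6.1 gives the same answer, since its relatedness line and its closing sentence are both limited to TEAEs.

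**Step 3: does anything else in the SAP fill the gap?** SAP 5.2 says in general terms that safety variables, AEs among them, will be summarised from all available data. It does not mention causality, and the specific list in 5.2.2 governs. Listings are named for protocol deviations (5.1.5), laboratory abnormalities and potential liver injury (5.2.3) and vital signs (5.2.4). None is named for AEs.

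**Step 4: does relatedness have meaning for a core AE?** The protocol treats it as meaningful. Section 3.1.1 uses the term IMP for the product of the previous trial when setting the 7-day interval. Section 5.7.3 makes SAEs reportable after the last scheduled contact if the investigator associates them with tolvaptan, so causality is expected to be judged when dosing is over.

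**The case against.** **The SAP is open about the missing data.** A reader might infer that the report will carry a relatedness table reading zero and suggest that no related events occurred. The documents do not support that. SAP 5.2 warns that not all planned safety analyses will be provided and withdraws those of the optional component. The natural reading is that the TEAE relatedness table is not produced, for a stated reason. What remains is an omission: nothing replaces it for core AEs.

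**The meaning of the recorded judgement is uncertain.** A reader might infer that a related core AE means one attributed to tolvaptan from the previous trial. The documents do not establish this. Protocol 5.1 refers to the IMP and Protocol 9.2 to tolvaptan, and neither tells investigators which exposure to judge in a subject not dosed here. Entry requires enrollment in a previous trial, not documented dosing. SAP 5.2 names tolvaptan in an earlier trial when defining baseline, but that does not show what investigators understood. This objection stands and limits the fix: the judgement should be reported as recorded, not given a meaning afterwards.

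**Causality may not be on the eCRF.** Protocol 9.2 places it in the progress notes and says generally that information from them is transcribed. Protocol 5.1 mentions the eCRF for severity but not for causality. A field is likely but not shown.

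**Important events are partly covered.** Core AEs still appear in five summaries. The liver injury table and listing in SAP 5.2.3 do not depend on treatment emergence, and Protocol 5.3 requires SAEs and potential liver injury to be reported within 24 hours. It would be wrong to infer that a serious delayed event would go unseen. None of this supplies a causality summary.

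**Conclusion.** The point holds as a reporting gap. By the SAP's own definition and its own statement about dosing, the relatedness line has no events, and none of the six planned summaries and no named listing shows causality for core AEs. That follows from a stated rule, not from missing detail, and it affects the component whose purpose is to follow the safety of tolvaptan.

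The size can be stated only structurally: 0 of 6 lines. The documents give neither the number enrolled nor the number of AEs judged related, so they do not support a claim that related events have been hidden. No primary or inferential result changes. The change is worth making because it is cheap and a related count is informative even if it is zero, provided it comes from the population actually followed.

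The conclusion assumes that SAP 5.2 is accurate that nobody was dosed, that causality was recorded for core AEs as Protocol 9.2 requires, and that no AE listing is planned outside the documents reviewed.

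**What to change.** Change the SAP only; no protocol amendment is needed.

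1. In 5.2.2, make the relatedness line match its five neighbours, so that it reads: AEs and "TEAEs potentially causally related to the IMP". Tabulate it on the Core Dataset.
2. Add an AE listing showing seriousness, severity, outcome and the causality the investigator recorded. Further breakdowns of related events are unnecessary, because the listing lets a reader cross-classify them.
3. Footnote both outputs: no subject was dosed in this trial, any tolvaptan given as study drug was given in the previous trial, and causality is shown as recorded. Do not redefine the judgement after collection.

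The cost is one table and one listing, from data that should already be held once the causality field is confirmed. The downsides are a possible non-zero related count and some remaining ambiguity about which exposure investigators judged, which the footnote discloses but cannot resolve.

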5.2.3 Laboratory Test Results

Summary statistics for the clinical laboratory measurements at baseline and post-baseline visits, and summary statistics of changes from baseline to each visit will be presented. Shift tables will be produced, assessing low-normal-high (at baseline) to low-normal-high (at post-baseline visit).

The incidence of potentially clinically significant abnormal lab results will also be summarized. Listings of potentially clinically significant abnormalities will also be provided.

According to FDA (Food and Drug Administration) Guidance,¹ laboratory measurements that signal the potential for drug-induced liver injury (DILI) will be reported. An incidence table and a listing will be provided for subjects who meet one or combinations of the following criteria:

- 1) ALT (alanine transaminase) or AST (aspartate transaminase) $\geq 3x$ upper limit of normal (ULN) (or baseline value for subjects with abnormal baseline)
- 2) Increase in bilirubin $\geq 2x$ ULN (or baseline value for subjects with abnormal baseline)

5.2.4 Vital Signs Data

Descriptive statistics will be provided for both vital signs and change from baseline in vital signs. The incidence of potentially clinically significant vital sign results will also be summarized. Listings of potentially clinically significant abnormalities will also be provided.

For a subject with repeat measures in either vital signs or lab tests at a visit, the last repeat will be used in the by visit summary. However, for outlier analysis (such as clinically significant abnormalities), data from all visits, no matter they are from the original visits, repeats, or unscheduled visits, will be included.

5.2.5 Electrocardiogram Data

Electrocardiogram (ECG) data will not be summarized since there are no trial mandated ECGs.

5.2.6 Post-baseline Concomitant Medications

Concomitant medications used post-baseline will be summarized in two categories of time interval: during the trial medication period and after the trial medication period. In each case, the use of concomitant medications will be summarized by number and percentage of users.

6 SAP References

- ¹ Guidance for Industry, Drug-Induced Liver Injury: Premarketing Clinical Evaluation. US Department of Health and Human Services, Food and Drug Administration, and Center for Drug Evaluation and Research (CDER), July 2009.

Otsuka Pharmaceutical Development & Commercialization, Inc.
This page is a manifestation of an electronically captured signature

OPC-41061

SIGNATURE PAGE

Document Name: SAP1561129414

Document Number: 0001163416

Document Version: 2.0

Signed by	Meaning of Signature	Server Date <small>(dd-MMM-yyyy HH:mm 'GMT'Z)</small>
PPD	Clinical Approval	23-Oct-2017 16:23 GMT+00
	Biostatistics Approval	23-Oct-2017 21:09 GMT+00
